#### 6 Treatment

## 6.1 Study treatment

In this study, the term "study treatment or drug" refers to Novartis study drug dabrafenib (DRB436) with trametinib (TMT212) or carboplatin and vincristine.

Refer to Section 6.1.1.1 for dabrafenib (DRB436) and trametinib (TMT212) dosing instructions. Refer to Section 6.1.2 for carboplatin and vincristine dosing instructions.

All dosages prescribed and dispensed to the patient and all dose changes during the study must be recorded on the Dosage Administration Record eCRF.

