|                                | 
 
Provide supportive care according
to institutional standards.
 
                        | 
 
Restart with dabrafenib and trametinib
reduced by one dose level once
toxicity resolves to ≤ Grade 1 or
baseline or permanently discontinue
dabrafenib and trametinib at the
discretion of investigator.
 
     |

These are general guidelines and investigators should always use clinical judgment in adverse event management for any individual patient. Some toxicities may require hospitalization for stabilization, additional work-up, and consultation with a specialist before treatment can be restarted. Investigators should always err on the side of caution in these settings if treatment

related toxicity is a possibility. All dose modifications are based on the worst preceding toxicity using Common Terminology Criteria for Adverse Events (CTCAE) Version v4.03.

If treatment related toxicities occur that are specific to combination treatment of dabrafenib and trametinib, then both treatments should be simultaneously dose reduced, interrupted or discontinued with the exception shown below:

Exception where dose modifications are necessary for **only dabrafenib**:

- Uncomplicated pyrexia (Table 6-16)
- Uveitis (Table 6-21)

Exception where dose modifications are necessary for **only trametinib**:

- Retinal vein occlusions (RVO) (Table 6-19) and retinal pigment epithelial detachment (RPED) Table 6-20)
- Left ventricular ejection fraction (LVEF) reduction (Table 6-23)

If the patient requires a dose interruption of > 28 days (greater than 6 weeks for uveitis, iritis, see Table 6-21) from the previous dose for persistent grade 2 or greater dabrafenib and/or trametinib treatment related toxicity, then the patient must be discontinued from study treatment. Up to two dose reductions will be allowed.

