Table 6-21 Mandatory dose modification and recommended clinical management for uveitis, including iritis suspected to be related to dabrafenib treatment

| Grade           | Recommended adverse event management guidelines                | Mandatory dose modification requirements   |
|-----------------|--|--|
| Grade 1         | Initiate local therapy and consult ophthalmologist immediately | 
 
Continue dabrafenib and trametinib
 
If no response to local treatment within 7 days, interrupt dabrafenib. Once uveitis resolves, restart dabrafenib
 
Continue trametinib
 
  |
| Grade 2, 3 or 4 | Initiate local therapy and consult ophthalmologist immediately | 
 
Interrupt dabrafenib
 
If ≥ grade 2 uveitis (including iritis and iridocylitis) lasts >6 weeks on local treatment and dabrafenib has not been restarted, permanently discontinue dabrafenib
 
Continue trametinib
 
 |

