#### QTc Prolongation QTcF ≥501 msec Based on average QTc value of triplicate ECGs

#### **Action and Dose Modifications**

- Assess the quality of the ECG recording and the QT value and repeat if needed
- Interrupt dabrafenib and trametinib (study treatments) until QTcF prolongation resolves to Grade 1 or baseline
- Test serum potassium, calcium, phosphorus and magnesium. If abnormal, correct per routine clinical practice to within normal limits.
- Review concomitant medication associated with QT prolongation, including drugs with a "known", "possible" or "conditional risk of Torsade de pointes" and drugs with the potential to increase the risk of study drug exposure related to QT prolongation
- If event resolves to grade 1 or baseline, patient may restart study treatments at current dose level if patient may benefit from further treatment
- If event does not resolve within 28 days, permanently discontinue study treatments. Consider evaluation with cardiologist.
- If event recurs, permanently discontinue study treatments. Consider evaluation with cardiologist.

Abbreviations: ECG = electrocardiogram; msec = milliseconds; QTcF = QT duration corrected for heart rate by Fredericia formula.

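### For uveitis interruptions beyond 6 weeks, Section 6.3.1 stops both drugs, while Table 6-21, which it cites, stops only dabrafenib and continues trametinib

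*Protocol*

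**What the plan says.** Four parts of the protocol bear on this.

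- **Section 6.3.1, length of interruption.** The general limit is 28 days. The parenthesis for eye inflammation reads "greater than 6 weeks for uveitis, iritis, see Table 6-21) from the previous dose". For persistent related toxicity of grade 2 or greater, the consequence is "dabrafenib and/or trametinib treatment related toxicity, then the patient must be discontinued from study treatment".
- **Section 6.1.** The term study treatment "refers to Novartis study drug dabrafenib (DRB436) with trametinib (TMT212) or carboplatin and vincristine".
- **Section 6.3.1, single-drug exceptions.** For toxicities specific to the combination, "then both treatments should be simultaneously dose reduced, interrupted or discontinued with the exception shown below". Under the heading for dabrafenib alone, the list includes "Uveitis (Table 6-21").
- **Table 6-21 (Section 6.3.1.4), mandatory column, grades 2 to 4.** Dabrafenib is interrupted. If uveitis of grade 2 or greater goes past 6 "weeks on local treatment and dabrafenib has not been restarted, permanently discontinue dabrafenib". The next instruction is "Continue trametinib".

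**The concern.** Two mandatory instructions cover the same child at about the same time and order different things for trametinib. One of them names the other as its source. The word must in Section 6.3.1 leaves no discretion, and the column of Table 6-21 that holds the conflicting order is headed as mandatory.

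If the Section 6.3.1 sentence is followed literally, a child with prolonged uveitis, which the protocol attributes to dabrafenib, also loses trametinib, the drug that Table 6-21 says to keep. Leaving study treatment then has consequences. Under Section 7.1.4 the end-of-treatment visit follows and tumour imaging continues every 16 weeks. The child also counts as having discontinued for the 32-week condition that triggers the primary analysis. Section 12 allows no authorised deviations, so a site that follows either text departs from the other.

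**Working it through.** The point concerns wording; no power, alpha or sample-size figure is involved. The check is to see whether the two texts can both be obeyed.

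1. **Same event?** The Section 6.3.1 sentence covers persistent related toxicity of grade 2 or greater and names uveitis and iritis. The relevant row of Table 6-21 covers uveitis of grades 2, 3 and 4. The events match.

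2. **Does an interruption of dabrafenib alone trigger the Section 6.3.1 rule?** It must. Table 6-21 never interrupts trametinib for uveitis at any grade. If the rule needed both drugs to be on hold, its uveitis parenthesis could never apply to a child managed by the table it cites.

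3. **Same time?** Both use 6 weeks: 6 × 7 = 42 days. The clocks are worded differently. Section 6.3.1 counts from the previous dose, and Table 6-21 counts how long the uveitis lasts on local treatment without dabrafenib being restarted. They run close together, because the table calls for dabrafenib to be interrupted once uveitis reaches grade 2. Once both have passed 42 days, both instructions are in force.

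4. **Same action?** No.
   - Dabrafenib: stopped under both texts.
   - Trametinib: stopped under Section 6.3.1 read with Section 6.1; continued under Table 6-21.

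5. **Which is intended?** Section 6.3.1 puts uveitis on its dabrafenib-only list, and the exception on that list extends to discontinuation as well as to reduction and interruption. With the cross-reference, this points to Table 6-21 as the intended instruction.

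6. **Does the conflict extend to other single-drug stops?** Table 6-18 (pneumonitis, grades 2 and 3) and Table 6-23 (asymptomatic LVEF decrease) stop trametinib permanently when there is no recovery within 4 weeks: 4 × 7 = 28 days. The Section 6.3.1 rule needs more than 28 days. A permanent stop at day 28 ends the interruption before that limit is passed, so these tables and the rule can be read together.

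7. **How many children does the rule govern?** With 2:1 randomisation of 102 LGG patients, 102 × 2/3 = 68 receive dabrafenib plus trametinib and 102 − 68 = 34 receive chemotherapy. Adding the HGG cohort gives 40 + 68 = 108 children, and at most 108 + 34 = 142 if every control patient crosses over. These are the children under the rule. The number with uveitis beyond 6 weeks cannot be derived, because the protocol states no uveitis rate.

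**The case against.** The best defence is that the protocol largely settles the uveitis case itself. The exception list limits modification to dabrafenib, the disputed sentence points to Table 6-21, and a site that follows the reference finds the instruction to continue trametinib. This stands as evidence of intent. It does not remove the contradiction: the discontinuation sentence comes after the exception list, names uveitis again, and uses the defined term without limiting it to the drug at fault. The remark in Section 6.3.1 about clinical judgement does not settle it either. It accompanies the general guidelines of Table 6-11, which apply where no specific guideline does, and the same text asks investigators to err on the side of caution.

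A reader might also infer three stronger points that the documents do not support.

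- **That the general sentence is wrong as a whole.** It might seem that an event table says so whenever both drugs must stop. Table 6-22 does: "If event does not resolve within 28 days, permanently discontinue study treatments". But Tables 6-11, 6-17 and 6-24 interrupt both drugs until recovery and give no time limit on the interruption. For those events the Section 6.3.1 sentence supplies the only limit, so it is needed.
- **That the sentence also cancels the single-drug options for pneumonitis and LVEF decrease.** As step 6 shows, a consistent reading exists. LVEF reduction is also on the trametinib-only list, and the asymptomatic row gives no CTCAE grade, so even the rule's grade 2 trigger would have to be inferred there.
- **That single-drug continuation should become the default.** For pancreatitis (Section 6.3.1.12) dabrafenib is held until recovery while trametinib may go on, with no time limit. A default of that kind would turn a long hold there into trametinib monotherapy. The uveitis conflict gives no support for that policy.

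**Conclusion.** The contradiction is real and confined to uveitis and iritis of grade 2 or greater with dabrafenib off for more than 6 weeks. Followed as written, Section 6.3.1 removes trametinib from a child for whom another mandatory rule orders it continued. The conclusion rests on reading study treatment as Section 6.1 defines it, and on the two 6-week clocks running nearly together.

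The practical weight is modest. The number of affected children is unknown and likely small, the intended instruction can be found, and the effect on ORR is negligible. Section 10.3 already summarises dose changes and discontinuations for each drug separately, so a single-drug stop needs no change to the analysis. Correction is still worthwhile because both texts are mandatory dosing instructions for children and the repair is small.

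**What to change.** Keep the general 28-day rule in Section 6.3.1 as the backstop and add directly after it:

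*For uveitis/iritis of grade 2 or greater lasting more than 6 weeks, only dabrafenib is permanently discontinued and trametinib continues per Table 6-21. Where Table 6-18 or Table 6-23 (asymptomatic LVEF decrease) directs permanent discontinuation of trametinib alone at 4 weeks, that table governs and this rule does not require stopping dabrafenib.*

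The first sentence removes the contradiction. The second fixes the consistent reading of Tables 6-18 and 6-23 so that sites do not have to work it out. Table 6-22 and the events without a time limit of their own are unaffected.

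The cost is two sentences in the next amendment, with no new procedures, data or analyses.

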#### **Dabrafenib Dosing Tables**

- Patients <12 years old and ≥16 kg may be administered either the dabrafenib capsules (Table 6-1) or dabrafenib dispersible tablets for oral suspension (Table 6-3)
- Patients ≥12 years old and ≥19 kg may be administered either the dabrafenib capsules (Table 6-2) or dabrafenib dispersible tablets for oral suspension (Table 6-4)
- Patients <12 years old and <16 kg **must** be administered dabrafenib dispersible tablets for oral suspension (Table 6-3)

• Patients ≥12 years old and <19 kg **must** be administered dabrafenib dispersible tablets for oral suspension (Table 6-4)

Table 6-1 Dose and treatment schedule for dabrafenib (DRB436) capsules for patients less than 12 years of age (5.25 mg/kg/day)

| Weight       | Dose   | Frequency and/or Regimen | Total Daily Dose | Pharmaceutical form and route of administration |
|--------------|--------|--------------------------|------------------|---|
| 16-23.5 kg   | 50 mg  | b.i.d                    | 100 mg           | Capsules for oral administration                |
| 23.6-33.5 kg | 75 mg  | b.i.d                    | 150 mg           | Capsules for oral administration                |
| 33.6-42.5 kg | 100 mg | b.i.d                    | 200 mg           | Capsules for oral administration                |
| 42.6-52.5 kg | 125 mg | b.i.d                    | 250 mg           | Capsules for oral administration                |
| ≥52.6 kg     | 150 mg | b.i.d                    | 300 mg           | Capsules for oral administration                |

Table 6-2 Dose and treatment schedule for dabrafenib (DRB436) capsules for patients greater or equal 12 years of age (4.5 mg/kg/day)

| Weight       | Dose   | Frequency and/or
Regimen | Total Daily
Dose | Pharmaceutical form and route of administration |
|--------------|--------|-----------------------------|---------------------|---|
| 19-27.5 kg   | 50 mg  | b.i.d                       | 100 mg              | Capsules for oral administration                |
| 27.6-38.5 kg | 75 mg  | b.i.d                       | 150 mg              | Capsules for oral administration                |
| 38.6-50.5 kg | 100 mg | b.i.d                       | 200 mg              | Capsules for oral administration                |
| 50.6-61.5 kg | 125 mg | b.i.d                       | 250 mg              | Capsules for oral administration                |

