| 33-49.5 kg   | 2 X 0.5 mg | q.d                      | 1 mg                | Tablets for oral administration                 |  |  |
| 49.6-69.5 kg | 3 X 0.5 mg | q.d                      | 1.5 mg              | Tablets for oral administration                 |  |  |
| ≥69.6 ka     | 1 X 2 ma   | a.d                      | 2 ma                | Tablets for oral administration                 |  |  |

The investigator or responsible site personnel should instruct the patient and guardians to take the study drug as per protocol (promote compliance).

If a patient's weight changes by more than the allowed institutional standard (or 10% if no institutional standard), the patient's administered dose may be adjusted based on the current weight of the patient using protocol Table 6-1 through Table 6-8.

If a patient has increased in weight and is tolerating the current dose administered, the protocol dosing Table 6-1 through Table 6-8 should be consulted to determine if a higher dose should be given. Otherwise, it is optional to consider if a higher dose should be administered.

If the patient has decreased in weight, they may continue on the current administered dose if it is tolerated. However, if the current administered dose is not tolerated, then the protocol dosing Table 6-1 through Table 6-8 should be consulted to determine if a lower dose should be given. Otherwise, it is optional to consider if a lower dose should be administered.

Protocol No. CDRB436G2201

If a patient's weight should fall below the lowest weight specified in Table 6-1 through Table 6-8, and per investigator the patient requires a lower administered dose (i.e., not tolerating current dose) then the dose specified in dose modification Table 6-12 through Table 6-15 should be utilized.

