#### 6.1.1.1 Dabrafenib (DRB436) and trametinib (TMT212) dosing

Study medications should be taken as follows:

- Dabrafenib will be administered twice daily per the dosing regimen shown in Table 6-1, Table 6-2, Table 6-3 and Table 6-4.
- Trametinib will be administered once daily per the dosing regimen shown in Table 6-5, Table 6-6, Table 6-7 and Table 6-8.
- Trametinib should be taken in combination with dabrafenib once daily, preferably in the morning.
- Dabrafenib capsules and trametinib tablets should be taken with approximately 120-240 mL of water.
- Trametinib pediatric oral solution formulation will be administered with a graduated syringe. Please refer to the trametinib oral solution Instructions for Use.
- Dabrafenib pediatric oral suspension formulation administration will be administered using dosing cup and/or graduated syringe. Please refer to dabrafenib oral suspension Instructions for Use.
- Refer to the dabrafenib and trametinib Instructions for Use documents if enteral feeding tubes are required for administering pediatric oral solutions.
- Patients less than 12 years of age who weigh less than 16 kg must be administered the dabrafenib dispersible tablets for oral suspension.
- Patients equal to or greater than 12 years of age who weigh less than 19 kg must be administered the dabrafenib dispersible tablets for oral suspension.
- Patients less than 6 years old who weigh less than 26 kg must be administered the trametinib oral solution.
- Patients older than 6 years old must weigh at least 33 kg to be administered the trametinib tablets.
- Patients should be encouraged to take dabrafenib at approximately 12 hour intervals and at similar times each day.
- Study treatment should be administered under fasting conditions, at least 1 hour before or 2 hours after a meal.
- If it is not possible for a patient to tolerate the fasting conditions noted above, study treatment may be administered with a small non-fat meal (e.g. small amount of apple juice/sauce, a piece of dry toast). Patients and their guardians should be advised to avoid administering study drug with milk or high-fat, high-calorie foods.
- Patients who are being breastfed may continue to be breastfed on demand. If the patient is breastfed during collection of PK samples the time of breastfeeding should be recorded as a meal.

- If a patient vomits after taking study drug, the patient should be instructed not to retake the dose and wait for the next scheduled dose.

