Dose reductions will occur in increments of 50 mg from the total daily dose for dabrafenib capsules and in increments of 0.5 mg from the total daily dose for trametinib tablets. If a patient is receiving trametinib 0.05 mg/mL oral solution, dose modification guidelines in Table 6-12 and Table 6-13 should be followed. If patient is receiving dabrafenib dispersible tablet, dose modification guidelines in Table 6-14 and Table 6-15 should be followed. If more than two dose reductions are needed, the patient must be discontinued from study treatment. Patients who discontinue study treatment due to adverse event will be followed until resolution or stabilization of the event. All dose changes and the reason for dose interruption must be recorded on the Dosage Administration Record eCRF.

Table 6-12 Dose Modification for trametinib (TMT212) oral solution for patients greater or equal to 6 years old

| Weight (kg) | Dose |       | Dose Redu
Level 1 | ıction | Dose reduction
Level 2 |        |
|-------------|------|-------|----------------------|--------|---------------------------|--------|
|             | mL   | mg    | mL                   | mg     | mL                        | mg     |
| 10-12.5     | 5    | 0.25  | 3.5                  | 0.175  | 2.5                       | 0.1225 |
| 12.6-16.5   | 7.5  | 0.375 | 5                    | 0.25   | 3.5                       | 0.175  |
| 16.6-24.5   | 10   | 0.5   | 7                    | 0.35   | 5                         | 0.25   |
| 24.6-35     | 15   | 0.75  | 10                   | 0.5    | 7                         | 0.35   |
| 35.1-45     | 20   | 1.0   | 14                   | 0.7    | 10                        | 0.5    |
| 45.1-55     | 25   | 1.25  | 17.5                 | 0.875  | 12                        | 0.6    |
| 55.1-68     | 30   | 1.5   | 20                   | 1      | 14                        | 0.7    |
| 68.1-72     | 35   | 1.75  | 25                   | 1.25   | 17.5                      | 0.875  |
| >72         | 40   | 2     | 28                   | 1.4    | 20                        | 1      |

Dose: 0.025 mg/kg/day
Dose Level 1: ~30% reduction

Dose Level 2: ~30% reduction

| Weight
(kg) | Dose |       | Dose Re
Level 1 | eduction | Dose redu
Level 2 | ction  |
|----------------|------|-------|--------------------|----------|----------------------|--------|
|                | mL   | mg    | mL                 | mg       | mL                   | mg     |

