| ≥55.6 kg    | 150 mg       | 140 mg                         | 130 mg                         |

Dose: 5.25 mg/kg/day Dose level 1: 4.5 mg/kg/day Dose level 2: 3.75 mg/kg/day

**Table 6-15** Dose Modification for dabrafenib (DRB436) dispersible tablet for patients greater or equal 12 years of age

| Weight    | Dose (b.i.d) | Dose Reduction Level 1 (b.i.d) | Dose Reduction Level 2 (b.i.d) |
|-----------|--------------|--------------------------------|--------------------------------|
| 10-11.5   | 20 mg        | 10 mg                          | 0 mg                           |
| 11.6-17.5 | 30 mg        | 20 mg                          | 10 mg                          |
| 17.6-20.5 | 40 mg        | 30 mg                          | 20 mg                          |
| 20.6-24.5 | 50 mg        | 40 mg                          | 30 mg                          |

| 24.6-28.5 | 60 mg  | 50 mg  | 40 mg  |
|-----------|--------|--------|--------|
| 28.6-32.5 | 70 mg  | 60 mg  | 50 mg  |
| 32.6-36.5 | 80 mg  | 70 mg  | 50 mg  |
| 36.6-40.5 | 90 mg  | 80 mg  | 60 mg  |
| 40.6-43.5 | 100 mg | 90 mg  | 60 mg  |
| 43.6-47.5 | 110 mg | 100 mg | 70 mg  |
| 47.6-51.5 | 120 mg | 110 mg | 80 mg  |
| 51.6-55.5 | 130 mg | 120 mg | 80 mg  |
| 55.6-64.5 | 140 mg | 130 mg | 100 mg |
| ≥64.6     | 150 mg | 140 mg | 110 mg |
|           |        |        |        |

Dose: 4.5 mg/kg/day
Dose level 1: 3.75 mg/kg/day
Dose level 2: 3.00 mg/kg/day

If a patient's dose of dabrafenib and trametinib has been reduced per the dose modification instructions, dose re-escalation may be considered provided the following criteria are met:

- A period of 4 weeks of treatment have passed since restarting dosing at the lower dose level and treatment has been well tolerated
- Patient is deriving clinical benefit

Dose re-escalation follows the same dosing steps as de-escalation, in increments of 50 mg from the total daily dose for dabrafenib capsules and in increments of 0.5 mg from the total daily dose for trametinib tablets. Patients receiving trametinib 0.05 mg/mL oral solution are to follow Table 6-12 and Table 6-13 for dose re-escalation. Patients receiving dabrafenib dispersible tablet are to follow Table 6-14 and Table 6-15 for dose re-escalation. The dabrafenib dose must not exceed 150 mg twice daily (300 mg total daily dose). The trametinib dose must not exceed 2 mg once daily.

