## 6.6.1 Study treatment packaging and labeling

Study treatment, dabrafenib (DRB436) and trametinib (TMT212), will be provided as global clinical open-labelled supply or commercially sourced supply. Global supplies will be packed and labeled under the responsibility of Novartis Drug Supply Management. Commercially sourced supplies will be packed and labeled as per local regulations.

Dabrafenib and trametinib in different formulations and strengths can be used once a protocol amendment with additional formulation description is approved.

Study treatment labels will comply with the legal requirements of each country and will include storage conditions, and Novartis Drug Supply Management supplied treatment will also contain a unique medication number (corresponding to study treatment and strength).

Table 6-26 Packaging and labeling

| Study treatments                  | Packaging                          | Labeling                           |
|-----------------------------------|------------------------------------|------------------------------------|
| DRB436 50mg                       | Capsules in bottles                | DRB436 50mg HPMC                   |
| DRB436 75mg                       | Capsules in bottles                | DRB436 75mg HPMC                   |
| DRB436 10mg                       | Dispersible tablets in bottles     | DRB436 10mg                        |
| TMT212 0.5 mg                     | Tablets in bottles                 | TMT212 0.5 mg FCT                  |
| TMT212 2.0 mg                     | Tablets in bottles                 | TMT212 2.0 mg FCT                  |
| TMT212 PIB 5mg                    | Powder in bottle                   | TMT212 PIB 5mg FMI                 |
| Carboplatin 175 mg/m  | Refer to local product information | Refer to local product information |
| Vincristine 1.5 mg/m  | Refer to local product information | Refer to local product information |

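### The mandatory 50 mg/day reduction step for dabrafenib capsules calls for 25 mg b.i.d. at the two lowest starting doses, which the supplied 50 and 75 mg capsules cannot provide

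*Protocol*

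**What the plan says.** Section 6.3.1 sets the capsule step: "Dose reductions will occur in increments of 50 mg from the total daily dose for dabrafenib capsules and in increments of 0.5 mg" for trametinib tablets. It also says "Up to two dose reductions will be allowed". The section's opening text mandates interruption or modification for patients who do not tolerate the schedule, and Table 6-11 lists the reductions in its column of mandatory requirements.

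For the other formulation, "If patient is receiving dabrafenib dispersible tablet, dose modification guidelines in Table 6-14 and Table 6-15 should be followed". The re-escalation paragraph repeats the capsule step: "Dose re-escalation follows the same dosing steps as de-escalation, in increments of 50 mg from the total daily dose for dabrafenib capsules".

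Section 6.1.1 lets sites choose the formulation at these weights: "Patients <12 years old and ≥16 kg may be administered either the dabrafenib capsules (Table 6-1) or dabrafenib dispersible tablets", with a matching line for patients from 12 years and 19 kg. On frequency, Section 6.1.1.1 states "Dabrafenib will be administered twice daily per the dosing regimen shown in Table 6-1" and the tables that follow it, and Section 2.3 splits the daily dose into two equal parts. Table 6-26 lists dabrafenib as 50 mg capsules, 75 mg capsules and 10 mg dispersible tablets. Section 6.6.1 adds: "Dabrafenib and trametinib in different formulations and strengths can be used once a protocol amendment with additional formulation description is approved".

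Only one sentence sends patients to the tablet and solution reduction tables on other grounds. It applies to a patient who is not tolerating the dose and begins: "If a patient's weight should fall below the lowest weight specified in Table 6-1 through Table 6-8".

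**The concern.** A mandatory safety rule should always produce a dose that the site can dispense. At the two lowest capsule starting doses this one does not. A child on capsules who reaches a required reduction would need 25 mg per administration, and no capsule or combination of capsules contains that amount. A single 50 mg capsule per day would meet the daily total but break the twice-daily, equal-dose regimen.

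Sites would therefore improvise, and not all in the same way. The obvious improvisation is to move the child to dispersible tablets and read the dose from Table 6-14 or 6-15. Those tables are indexed by body weight, not by the dose that caused the toxicity, so the row a site lands on need not be lower than what the child was taking. What is at stake is a consistent and genuinely lower dose for a child recovering from toxicity. The statistical inference is not at stake.

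**Working it through.** **Inputs.** Step: 50 mg of total daily dose, at most two reductions (Section 6.3.1). Starting doses and weight bands: Tables 6-1 and 6-2. Strengths: 50 and 75 mg capsules, 10 mg dispersible tablet (Table 6-26). Frequency: twice daily (Section 6.1.1.1), in equal doses (Section 2.3).

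**Formula.** For a starting dose D mg b.i.d. at reduction level k, the dose per administration is (2D - 50k)/2 = D - 25k.

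| Start (mg b.i.d.) | Level -1 | Level -2 |
|---|---|---|
| 50 | 25, cannot be made | 0 |
| 75 | 50 | 25, cannot be made |
| 100 | 75 | 50 |
| 125 | 100 | 75 |
| 150 | 125 | 100 |

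Sums of 50 and 75 give 50, 75, 100 and 125, but not 25. Nor is 25 a multiple of 10, so the dispersible tablets cannot reproduce the step exactly either.

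**Bands affected.** Level -1 fails at 16-23.5 kg (<12 years) and 19-27.5 kg (≥12 years). Level -2 fails at 23.6-33.5 kg (<12 years) and 27.6-38.5 kg (≥12 years). That is 2 of 5 bands in Table 6-1 and 2 of 5 in Table 6-2, so 4 of 10.

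**What a switch through Tables 6-14 and 6-15 would give.** In both failing cases the child is on 50 mg b.i.d. immediately before the failing step (75 - 25 = 50 for the 75 mg starters). The same-level entry for the child's weight is compared with 50 mg b.i.d.

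| Failing step | Age | Weight (kg) | Table entry (mg b.i.d.) | Against 50 |
|---|---|---|---|---|
| Level -1 | <12 | 16-17.5 | 30 | lower |
| | | 17.6-20.5 | 40 | lower |
| | | 20.6-23.5 | 50 | unchanged |
| | ≥12 | 19-20.5 | 30 | lower |
| | | 20.6-24.5 | 40 | lower |
| | | 24.6-27.5 | 50 | unchanged |
| Level -2 | <12 | 23.6-24.5 | 40 | lower |
| | | 24.6-28.5 | 50 | unchanged |
| | | 28.6-32.5 | 60 | higher |
| | | 32.6-33.5 | 70 | higher |
| | ≥12 | 27.6-28.5 | 40 | lower |
| | | 28.6-36.5 | 50 | unchanged |
| | | 36.6-38.5 | 60 | higher |

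The upper part of every affected band returns an unchanged or higher dose in mg. In the two 75 mg bands only about the lowest kilogram returns a lower one.

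**The case against.** The strongest reply is that the child is not stranded. Every affected band is one where Section 6.1.1 permits either formulation, the 10 mg tablet is already supplied, and nothing forbids changing from one to the other. Once the child is on tablets, Tables 6-14 and 6-15 apply by their own terms. Section 6.3.1 also describes its general guidance as subject to clinical judgement. Much of this stands. A reader might infer that the protocol leaves no valid dose and forces these children off treatment, but the documents do not support that: a lower dispersible dose is physically available and permitted. What does not stand is that the tables then resolve the matter, because in much of the affected weight range they return the same or a higher dose in mg.

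A second reply is that a 0 mg second level is not a fault. That is right. Tables 6-14 and 6-15 themselves print 0 mg at level 2 for their lowest bands (7-9.5 kg and 10-11.5 kg), and the two-reduction allowance is a ceiling, not a promise of two non-zero levels. So each affected band has one undeliverable step. The 0 mg level from 50 mg b.i.d. is not a second failure.

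Two further readings are tempting and should be resisted. One is that trametinib tablets share the problem. They do not: 1 mg to 0.5 mg to 0 mg can be dispensed, and the zero level has the precedent just given. The other is to price the switch as a change in exposure using the lower bioavailability of the suspension. That figure in Section 1.2.1.3 comes from single doses, the protocol calls the difference not clinically relevant, and the same section reports less than dose-proportional exposure on repeated b.i.d. dosing. A steady-state exposure change cannot be derived from it.

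**Conclusion.** The defect holds as a dosing-feasibility gap and should be fixed. One mandatory step in each of 4 of the 10 capsule bands calls for 25 mg b.i.d., which cannot be made from the supplied capsules. No rule directs a switch of formulation, and the weight-keyed tablet tables are not a safe substitute. Starting doses of 100, 125 and 150 mg b.i.d. are unaffected.

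The conclusion rests on the strengths in Table 6-26 and on twice-daily dosing in equal parts. It bears only on children started on capsules at 50 or 75 mg b.i.d. who reach the failing step. The protocol gives no distribution of weight or formulation and no expected reduction rate, so their number cannot be estimated. A reader might infer that the primary result is at risk. Nothing supports that: the ORR comparison, its power and its error rate do not depend on this rule.

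**What to change.** In Section 6.3.1, for capsule patients who start at 50 or 75 mg b.i.d., state that the step which capsules cannot deliver is given by changing to the 10 mg dispersible tablets at a named dose strictly below the current one. An example, with the levels for the sponsor to set:

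- 50 mg b.i.d. capsule: 40, then 30 mg b.i.d. dispersible.
- 75 mg b.i.d. capsule: 50 mg b.i.d. capsule, then 40 mg b.i.d. dispersible.
- 100, 125 and 150 mg b.i.d.: keep the 50 mg/day step.

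Refer the re-escalation paragraph to the same rule.

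In choosing levels, the sponsor should note that a rule keyed to starting dose falls below the level 2 targets under Tables 6-14 and 6-15 (3.75 mg/kg/day under 12 years, 3.00 from 12 years) at the top of each band. For example, 30 mg b.i.d. is 60/23.5 = 2.6 mg/kg/day at 23.5 kg (<12 years) and 60/27.5 = 2.2 at 27.5 kg (≥12 years), and 40 mg b.i.d. is 80/33.5 = 2.4 at 33.5 kg (<12 years). The example is still milder than the present rule, which gives 25 mg b.i.d. or 0 at the same points.

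The cost is a short rule or table and a cross-reference in an amendment, using products already supplied. The downside is that some children must change formulation in order to reduce.
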